### 7.3.1 For Vitamin D Sufficient Patients

Age	All	Vitamin D	Calcium (elemental)
Vitamin D level (D 2 +D 3 ) T	sufficient	600 IU/day of Vitamin D supplementation only	No Supplementation
ionized or corrected calcium level	normal		
dietary calcium intake based on questionnaire	sufficient		

Age	1-3 years	Vitamin D	Calcium (elemental)
Vitamin D level (D 2 +D 3 ) T	sufficient	600 IU/day of Vitamin D	600 mg/day
ionized or corrected calcium level	normal		
dietary calcium intake based on questionnaire	low		

Age	4-8 years	Vitamin D	Calcium (elemental)
Vitamin D level (D 2 +D 3 ) T	sufficient	600 IU/day of Vitamin D	1,000 mg/day
ionized or corrected calcium level	normal		
dietary calcium intake based on questionnaire	low		

Age	≥ 9 years	Vitamin D	Calcium (elemental)
Vitamin D level (D 2 +D 3 ) T	sufficient	600 IU/day of Vitamin D	1,200 mg/day
ionized or corrected calcium level	normal		
dietary calcium intake based on questionnaire	low		

Age	1-3 years	Vitamin D	Calcium (elemental)
Vitamin D level (D 2 +D 3 ) T	sufficient	• 600 IU/day Vitamin D	• calcium supplementation at a dose of 50 mg/kg divided 3x/day day (max daily calcium dose of 2000 mg/day). • Check levels weekly, increase as needed to normalize ionized or corrected calcium. • Once normalized, if dietary calcium intake is low the participant would receive calcium 600 mg/day
ionized or corrected calcium level	low		
dietary calcium intake based on questionnaire	Low or normal		

Age	4-8 years	Vitamin D	Calcium (elemental)
Vitamin D level (D 2 +D 3 ) T	sufficient	• 600 IU/day Vitamin D	• calcium supplementation at 50 mg/kg divided 3x/day day (max daily calcium dose of 2000 mg/day). • Check levels weekly, increase as needed to normalize ionized or corrected calcium. • Once normalized, if dietary calcium intake is low the participant would receive calcium 1,000 mg/day
ionized or corrected calcium level	low		
dietary calcium intake based on questionnaire	Low or normal		

Age	$\geq 9$ years	Vitamin D	Calcium (elemental)
Vitamin D level ( $D_2+D_3$ ) f	sufficient	• 600 IU/day Vitamin D	• calcium supplementation at 50 mg/kg divided 3x/day (max daily calcium dose of 2000 mg/day).
ionized or corrected calcium level	low		• Check levels weekly, increase as needed to normalize ionized or corrected calcium.

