### 7.3.2 For Low vitamin D ( $D_2+D_3$ ) Levels

Age	$<9$	Vitamin D	Calcium (elemental)
Vitamin D level ( $D_2+D_3$ ) f	20-29	• 4000 IU/day of vitamin D supplementation x 4 weeks	• No supplementation
ionized or corrected calcium level	normal		
dietary calcium intake based on questionnaire	sufficient	• Vitamin D ( $D_2+D_3$ ) level should be checked in 4 or 8 weeks and continue supplementation if needed • Once the Vitamin D level is normalized the participant would receive 600 IU/day of Vitamin D	

Age	$\geq 9$	Vitamin D	Calcium (elemental)
Vitamin D level ( $D_2+D_3$ ) T	20-29	
 
• 4000 IU/day of vitamin D supplementation x 8 weeks
 
	
 
• No supplementation
 

ionized or corrected calcium level	normal	
 
• Vitamin D (<math>D_2+D_3</math>) level should be checked in 4 or 8 weeks and continue supplementation if needed
 
	
dietary calcium intake based on questionnaire	sufficient	
 
• Once the Vitamin D level is normalized the participant would receive 600 IU/day of Vitamin D
 
	

Age	1-3 Years	Vitamin D	Calcium (elemental)
Vitamin D level ( $D_2+D_3$ ) T	20-29	
 
• 4000 IU /day of vitamin D supplementation x 4 weeks
 
	
 
• calcium 600 mg/day
 

ionized or corrected calcium level	normal	
 
• Vitamin D (<math>D_2+D_3</math>) level should be checked in 4 or 8 weeks and continue supplementation if still low
 
	
dietary calcium intake based on questionnaire	low	
 
• Once the Vitamin D level is normalized the participant would receive 600 IU/day of Vitamin D
 
	

Age	4-8 years	Vitamin D	Calcium (elemental)
Vitamin D level (D 2 +D 3 ) T	20-29	
 
• 4000 IU/day of vitamin D supplementation x 4 weeks
 
• Vitamin D (D2+D3) level should be checked in 4 or 8 weeks and continue supplementation if still low
 
• Once the Vitamin D level is normalized the participant would receive 600 IU/day of Vitamin D
 
	
 
• calcium 1,000 mg/day
 

ionized or corrected calcium level	normal		
dietary calcium intake based on questionnaire	low		

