Age	$\geq 9$	Vitamin D	Calcium (elemental)
Vitamin D level (D 2 +D 3 ) T	20-29	
 
• 4000 IU/day of vitamin D supplementation x 8 weeks; or 50000 IU (single dose) of vitamin D every other week x 4 doses total
 
• Vitamin D (D2+D3) level should be checked in 4 or 8 weeks and continue supplementation if still low
 
• Once the Vitamin D level is normalized the participant would receive 600 IU/day of Vitamin D
 
	
 
• calcium 1,200 mg/day
 

ionized or corrected calcium level	low		
dietary calcium intake based on questionnaire	Low or normal		

Age	1-3 years	Vitamin D	Calcium (elemental)
Vitamin D level (D 2 +D 3 ) T	20-29	
 
4000 IU/day of vitamin D supplementation x 4 weeks
 
	
 
calcium supplementation at 50 mg/kg divided 3x/day day (max daily calcium dose of 2000 mg/day).
 

ionized or corrected calcium level	low	
 
Vitamin D (D2+D3) level should be checked in 4 or 8 weeks and continue supplementation if still low
 
	
 
Check levels weekly, increase as needed if low.
 

dietary calcium intake based on questionnaire	Low or normal	
 
Once the Vitamin D level is normalized the participant would receive 600 IU/day of Vitamin D
 
	
 
Once ionized or corrected calcium is normalized, if dietary calcium is low, the participant would receive calcium 600 mg/day
 

Age	4-8 years	Vitamin D	Calcium (elemental)
Vitamin D level (D 2 +D 3 ) T	20-29	
 
4000 IU/day of vitamin D supplementation x 4 weeks
 
	
 
calcium supplementation at 50 mg/kg divided 3x/day day (max daily calcium dose of 2000 mg/day).
 

ionized or corrected calcium level	low	
 
Vitamin D (D2+D3) level should be checked in 4 or 8 weeks and continue supplementation if still low
 
	
 
Check levels weekly, increase as needed if low.
 

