dietary calcium intake based on questionnaire	Low or normal	
 
Once the Vitamin D level is normalized the participant would receive 600 IU/day of Vitamin D
 
	
 
Once ionized or corrected calcium is normalized, if dietary calcium is low, the participant would receive calcium 1,000 mg/day
 

Age	$\geq 9$	Vitamin D	Calcium (elemental)
Vitamin D level ( $D_2+D_3$ ) T	20-29	
 
4000 IU/day of vitamin D supplementation x 8 weeks; or 50000 IU (single dose) of vitamin D every other week x 4 doses total Vitamin D (<math>D_2+D_3</math>) level should be checked in 4 or 8 weeks and continue supplementation if still low
 
Once the Vitamin D level is normalized the participant would receive 600 IU/day of Vitamin D
 
	
 
calcium supplementation at a dose of 50 mg/kg divided 3x/day (max daily calcium dose of 2000 mg/day).
 
Check levels weekly, increase as needed if low.
 
Once ionized or corrected calcium is normalized, if dietary calcium is low, the participant would receive calcium 1,200 mg/day
 

ionized or corrected calcium level	normal		
dietary calcium intake based on questionnaire	low		

Age	$< 9$	Vitamin D	Calcium (elemental)
Vitamin D level ( $D_2+D_3$ ) T	20-29	
 
50000 IU (single dose) of vitamin D every other week x 2 doses total
 
Check Vitamin D (<math>D_2+D_3</math>) levels in 4 weeks
 
Continue vitamin D supplementation until Vitamin D levels normalize. Once normalized vitamin D would be given as part of multivitamin supplementation.
 
	
 
calcium supplementation at a dose of 50 mg/kg/day (max daily calcium dose of 2000 mg/day) or the maximum allowed per TPN
 
Check ionized or corrected calcium level every week
 

ionized or corrected calcium level	low		
Patient on TPN	Yes		

Age	$\geq 9$	Vitamin D	Calcium (elemental)
Vitamin D level ( $D_2+D_3$ ) T	20-29	
 
50000 IU (single dose) every other week x 4 doses total
 
	
 
calcium supplementation a dose of 50 mg/kg/day (max daily calcium dose of 2000 mg/day) or the maximum allowed per TPN
 

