ionized or corrected calcium level	low	
 
Check Vitamin D (<math>D_2+D_3</math>) levels in 8 weeks
 
Continue vitamin D supplementation until Vitamin D levels normalize. Once normalized vitamin D would be given as part of multivitamin supplementation.
 
	
 
Check ionized or corrected calcium level every week
 

Patient on TPN	Yes		

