PTH*	>65	
 
• 4000 IU/day of vitamin D supplementation x 8 weeks
 
• Vitamin D (D2+D3) level should be checked in 8 weeks
 
• continue Vitamin D supplementation if still low
 
• Once normalized the participant would receive 600 IU/day of Vitamin D
 
	
 
• calcium supplementation at a dose of 50 mg/kg divided 3x/day (max daily calcium dose of 2.000 mg/day) for 4 weeks
 
• Check ionized or corrected calcium level every week and increase supplementation as needed to normalize ionized or corrected calcium
 
• Once ionized or corrected calcium is normalized, if dietary calcium is low, the participant will receive calcium 1,000 mg/day
 

**\* When PTH is <65 and Vitamin D level (D2+D3) is 10-19 with low ionized or corrected calcium and normal or low dietary calcium intake, follow the same supplementation guidelines.**

Age	$\geq 9$	Vitamin D	Calcium (elemental)
Vitamin D level ( $D_2+D_3$ ) T	10-19	
 
• 50000 IU (single dose) every week x 8 total doses
 
• Vitamin D (<math>D_2+D_3</math>) level should be checked in 8 weeks
 
• Continue Vitamin D supplementation if still low
 
• Once normalized the participant would receive 600 IU/day of Vitamin D
 
	
 
• calcium supplementation at a dose of 50 mg/kg divided 3x/day (max daily calcium dose of 2.000 mg/day) for 4 weeks
 
• Check ionized or corrected calcium level every week and increase supplementation as needed to normalize ionized or corrected calcium
 
• Once ionized or corrected calcium is normalized, if dietary calcium is low, the participant will receive calcium 1,200 mg/day
 

ionized or corrected calcium level	low		
dietary calcium intake	normal or low		
PTH*	$>65$		

***\*When PTH is  $<65$  and Vitamin D level ( $D_2+D_3$ ) is 10-19 with low ionized or corrected calcium and normal or low dietary calcium intake, follow the same supplementation guidelines.***

Age	<9	Vitamin D	Calcium (elemental)

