**7.4 Pamidronate**

**7.4.1 Treatment Plan**

Subjects randomized to the Pamidronate Group will receive 3 single doses of pamidronate at 3-month intervals (Day 90 +/-14 days, Day 180 +/-14 days, and Day 270 +/-30 days).

Note: All time point specific laboratory testing procedures (sections 8.1 and 8.3) must be collected prior to the pamidronate infusion (except those specifically designated post infusion); however for ease of scheduling the consultations as well as the Day 90 DXA and Day 90 pQCT may be performed after the infusion as long as done within the +/-14 day window. Ionized calcium or corrected calcium, and Vitamin D levels (D2+D3) will be drawn prior to pamidronate infusions. If either are low, the subject should receive supplemental calcium and/or Vitamin D per Section 7.3. If the subject is receiving supplemental calcium, an ionized or corrected calcium level should be drawn after the pamidronate infusion end but prior to discharge from clinic on the day of the pamidronate.

Prior to each infusion the patient will be assessed and pamidronate will be held if:

- Serum creatinine is > 2 times the baseline (Study Entry) level – refer to section 7.3.2 for monitoring plan – the pre-treatment creatinine may be done anytime within 72 hours prior to the planned pamidronate administration

- Pregnancy test is positive (subject will permanently discontinue study drug) per section 7.3.5 – pregnancy testing may be done anytime within 72 hours prior to the planned pamidronate administration

Pamidronate 1 mg/kg (to a max dose of 60 mg) will be administered via a single IV infusion over 4 hours using a line separate from all other drugs. Dosing will be based on the patient's actual weight or, if overweight, on ideal body weight (IBW). This will be followed by a normal saline flush of 20 cc total given at the same rate as the pamidronate.

Premedication: Subjects will be given 15 mg/kg acetaminophen (or maximum of 500 mg) prior to pamidronate infusion then every 4 hours as needed for a maximum of 24 hours.

Post-Pamidronate Infusion Laboratory Tests: A serum calcium level will be done after the pamidronate infusion end but prior to discharge from clinic on the day of the pamidronate.

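### In section 7.3.2, two oral charts for age 9 and over have their calcium and diet labels crossed with their calcium regimens, so the low-calcium child gets a flat dose and no required weekly check

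*Combined protocol and SAP*

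**What the plan says.** Section 7.3 sets calcium supplementation by age, vitamin D level, calcium level and dietary intake. Two oral charts in 7.3.2 matter here. Both are for age 9 and over with vitamin D 20-29.

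- The chart labelled calcium low, diet low or normal prescribes only "calcium 1,200 mg/day". Its calcium cell has no recheck and no titration.
- The chart labelled calcium normal, diet low prescribes 50 mg/kg in three divided doses, capped at 2,000 mg/day, with weekly checks and increases if low. It ends: "Once ionized or corrected calcium is normalized, if dietary calcium is low, the participant would receive calcium 1,200 mg/day".

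For the same age and vitamin D band with low calcium on parenteral nutrition, 7.3.2 gives "calcium supplementation a dose of 50 mg/kg/day (max daily calcium dose of 2000 mg/day) or the maximum allowed per TPN" and adds "Check ionized or corrected calcium level every week". For age 4-8 with normal calcium and low diet, it gives a flat "calcium 1,000 mg/day".

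Section 7.4.1 requires calcium and vitamin D levels before each infusion: "If either are low, the subject should receive supplemental calcium and/or Vitamin D per Section 7.3". The opening note of 7.3 says the charts list ideal target doses and that actual dosing will lie in an acceptable range set by formulations and insurance.

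**The concern.** A step that waits for calcium to normalize has no meaning for a child whose calcium is normal. A child with low calcium, in turn, would be expected to have the level followed. Read together, the two charts appear to carry each other's labels.

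The point bears on safety. Section 7.4.3 names hypocalcaemia as a common side effect of pamidronate in children. Section 6.2 bars randomization when vitamin D is below 20 because of hypocalcaemia risk, so 20-29 is the lowest band admitted. The hold criteria in 7.4.1 are creatinine and pregnancy only. Low calcium does not hold the infusion, and the protocol's response to it is the 7.3 chart. Both arms use the charts from admission. Section 12.3 plans two thirds of enrolment below age 10, which leaves about one third at 10 or over, all within this age band.

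**Working it through.** The plan states no figure to reproduce. The check is a comparison of charts, followed by dose and visit arithmetic.

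**1. Oral charts side by side (7.3.1 and 7.3.2).** The apparent rule is a flat age-band dose for normal calcium with low diet, and 50 mg/kg with weekly checks for low calcium.

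| Section | Age | Labelled normal calcium, low diet | Labelled low calcium |
|---|---|---|---|
| 7.3.1 | 1-3 | flat 600 mg | 50 mg/kg, weekly |
| 7.3.1 | 4-8 | flat 1,000 mg | 50 mg/kg, weekly |
| 7.3.1 | 9 and over | flat 1,200 mg | 50 mg/kg, weekly |
| 7.3.2 | 1-3 | flat 600 mg | 50 mg/kg, weekly |
| 7.3.2 | 4-8 | flat 1,000 mg | 50 mg/kg, weekly |
| 7.3.2 | 9 and over | **50 mg/kg, weekly** | **flat 1,200 mg, no check** |

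Ten of the 12 follow the rule. The two that break it are the pair in question.

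**2. Wider tally.** Charts whose label includes low calcium: 3 in 7.3.1, 5 in 7.3.2 (3 oral, 2 parenteral nutrition) and 5 in 7.3.3 (3 oral, 2 parenteral nutrition labelled normal or low), 13 in all. Twelve give 50 mg/kg with weekly calcium checks. Charts for normal calcium with low diet in 7.3.1 and 7.3.2: 3 + 3 = 6, of which 5 give a flat dose. The oral normal-calcium charts of 7.3.3 are left out of the second tally because they require PTH above 65.

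**3. Which side was crossed.** The tallies show a mismatch but cannot say whether labels or regimens moved. Chart order can. In 7.3.2 the oral low-diet and low-calcium charts run 1-3, 4-8, 9 and over with flat doses, then 1-3, 4-8, 9 and over with 50 mg/kg. Each of the two charts holds the regimen that fits its position and the labels that fit the other's. This suggests the labels. Exchanging the calcium cells instead gives the same result.

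**4. Dose gap.** The documents give no weights, so those below are assumptions. The wording of 50 mg/kg in three divided doses is read as per day, which the daily cap and other charts support. Parallel-chart target = min(50 × kg, 2,000) mg/day. It equals 1,200 at 1,200/50 = 24 kg and reaches the cap at 2,000/50 = 40 kg.

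| Weight | Parallel target | Printed, low calcium | Difference |
|---|---|---|---|
| 24 kg | 1,200 | 1,200 | 0% |
| 30 kg | 1,500 | 1,200 | -300/1,500 = -20% |
| 35 kg | 1,750 | 1,200 | -550/1,750 = -31% |
| 40 kg and over | 2,000 | 1,200 | -800/2,000 = -40% |

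For the normal-calcium, low-diet child the comparison reverses: 1,500/1,200 = +25% at 30 kg and 2,000/1,200 = +67% from 40 kg.

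**5. Calcium checks.** Section 8.1 schedules calcium at Day 90 (±14) and next at Day 180 (±14).

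- Nominal gap: 180 − 90 = 90 days; 90/7 = 12.9, so 12 weekly checks.
- Shortest: 166 − 104 = 62 days; 62/7 = 8.9, so 8.
- Longest: 194 − 76 = 118 days; 118/7 = 16.9, so 16.

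These counts assume calcium stays low throughout; there are fewer if it normalizes sooner.

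**The case against.** Several points can fairly be made for the plan.

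- **The doses are targets.** The opening note of 7.3 allows an acceptable range. This stands: the percentages describe targets, not doses given.
- **The excess may not occur.** A prescriber with a normal-calcium child may treat the normalization step as already met and give 1,200 mg/day. This stands, so the +25% and +67% are conditional. The odd wording may also alert the prescriber to the slip.
- **Other monitoring exists.** The low-calcium chart rechecks vitamin D at 4 or 8 weeks, and a footnote in 8.3.1 puts total calcium in the same tube as vitamin D. Section 7.2 acts on a low calcium at any time, 7.4.3 refers to intensive post-transplant monitoring, and pamidronate patients have a same-day post-infusion calcium. These lower the practical risk. None replaces the weekly calcium check that the parallel charts require.
- **50 mg/kg with normal calcium has a precedent in 7.3.3.** Those oral charts require PTH above 65, step down after a fixed 4 weeks without weekly checks, and carry a footnote waiving the dose when PTH is below 65. The 7.3.2 chart has no PTH condition and covers a milder deficiency, so the precedent does not explain it.
- **A PDF-reading fault.** This is unlikely. Two complete charts lie between the pair, and the calcium and diet rows are exchanged together.

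A reader might also infer that the weight-based start needs a floor at the flat dose, since below 24 kg the 50 mg/kg figure is the smaller for this age group. That would be a new dosing rule. The documents give no basis for it, and the correction does not need it.

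**Conclusion.** The point holds as an internal inconsistency in a safety instruction that should be corrected. Two charts in 7.3.2 are the only exceptions to a pattern that every comparable chart follows, and nothing elsewhere in the protocol corrects them.

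The main consequence is the missing requirement for weekly calcium checks in the low-calcium child: about 12 between Day 90 and Day 180 at nominal timing, 8 to 16 across the windows, if calcium stays low. The dose shortfall is secondary. It rests on assumed weights and applies above 24 kg, reaching 800 mg/day from 40 kg.

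A reader might infer that children were under-treated or harmed, or that the trial's comparison is biased. The documents do not support either. They report no such outcome, both arms use the same charts, and neither the sample size nor the primary analysis depends on them.

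**What to change.** Exchange the calcium-level and diet labels on the two oral charts of 7.3.2 for age 9 and over with vitamin D 20-29. Low calcium (diet low or normal) then gets 50 mg/kg/day in three divided doses, maximum 2,000 mg/day, with weekly checks and the step-down to 1,200 mg/day if diet is low. Normal calcium with low diet gets 1,200 mg/day.

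The cost is one label correction on two charts. Their vitamin D cells carry the same regimen, so no vitamin D dose changes. Low-calcium children in this band gain weekly checks until normal, and normal-calcium children lose checks they do not need.

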### 7.3.3 Vitamin D Deficiency

Age	1-3 years	Vitamin D	Calcium (elemental)
Vitamin D level ( $D_2+D_3$ ) T	10-19	
 
4000 IU/day of vitamin D supplementation x 8 weeks. Vitamin D (<math>D_2+D_3</math>) level should be checked in 8 weeks
 
	
 
calcium supplementation at a dose of 50 mg/kg divided 3x/day (max daily calcium dose of 2000 mg/day) for 4 weeks
 

ionized or corrected calcium level	normal	
 
continue Vitamin D supplementation if still low
 
	
 
After 4 weeks of calcium supplementation, if dietary calcium is low, the participant will receive calcium 600 mg/day.
 

dietary calcium intake based on questionnaire	normal/low	
 
Once normalized the participant would receive 600 IU/day of Vitamin D
 
	
PTH*	$>65$		

\*When PTH is  $<65$  and Vitamin D level ( $D_2+D_3$ ) is 10-20 with normal ionized or corrected calcium and normal or low dietary calcium intake, calcium supplementation at a dose of 50mg/kg/day 3 times daily is not needed, otherwise follow the same supplementation guidelines.

Age	4-8 years	Vitamin D	Calcium (elemental)
Vitamin D level (D 2 +D 3 ) †	10-19	
 
4000 IU/day of vitamin D supplementation x 8 weeks. Vitamin D (D2+D3) level should be checked in 8 weeks
 
continue Vitamin D supplementation if still low
 
Once normalized the participant would receive 600 IU/day of Vitamin D
 
	
 
calcium supplementation at a dose of 50 mg/kg divided 3x/day (max daily calcium dose of 2000 mg/day) for 4 weeks
 
After 4 weeks of calcium supplementation, if dietary calcium is low, the participant will receive calcium 1,000 mg/day
 

ionized or corrected calcium level	normal		
dietary calcium intake based on questionnaire	normal/low		
PTH*	>65		

**\*When PTH is <65 and Vitamin D level (D2+D3) is 10-20 with normal ionized or corrected calcium and normal or low dietary calcium intake, calcium supplementation at a dose of 50mg/kg/day 3 times daily is not needed, otherwise follow the same supplementation guidelines.**

Age	≥9	Vitamin D	Calcium (elemental)
Vitamin D level (D 2 +D 3 ) †	10-19	
 
50000 IU (single dose) every week x 8 doses total
 
Vitamin D (D2+D3) level should be checked in 8 weeks
 
continue Vitamin D supplementation if still low
 
Once normalized the participant would receive 600 IU/day of Vitamin D
 
	
 
calcium supplementation at a dose of 50 mg/kg divided 3x/day (max daily calcium dose of 2,000 mg/day) for 4 weeks
 
After 4 weeks of calcium supplementation, if dietary calcium is low, the participant will receive calcium 1,200 mg/day
 

ionized or corrected calcium level	normal		
dietary calcium intake based on questionnaire	normal/low		
PTH*	>65		

**\*When PTH is <65 and Vitamin D level (D2+D3) is 10-20 with normal ionized or corrected calcium and normal or low dietary calcium intake, calcium supplementation at a dose of 50mg/kg/day 3 times daily is not needed, otherwise follow the same supplementation guidelines.**

Age	1-3 years	Vitamin D	Calcium (elemental)
Vitamin D level (D 2 +D 3 ) f	10-19	• 4000 IU/day of vitamin D supplementation x 8 weeks	• calcium supplementation at a dose of 50 mg/kg divided 3x/day (max daily calcium dose of 2.000 mg/day) for 4 weeks
ionized or corrected calcium level	low	• Vitamin D (D 2 +D 3 ) level should be checked in 8 weeks	• Check ionized or corrected calcium level every week and increase supplementation as needed to normalize ionized or corrected calcium
dietary calcium intake	normal or low	• continue Vitamin D supplementation if still low	• Once ionized or corrected calcium is normalized, if dietary calcium is low, the participant will receive calcium 600 mg/day
PTH*	>65	• Once normalized the participant would receive 600 IU/day of Vitamin D	

\* When PTH is <65 and Vitamin D level (D2+D3) is 10-19 with low ionized or corrected calcium and normal or low dietary calcium intake, follow the same supplementation guidelines.

Age	4-8 years	Vitamin D	Calcium (elemental)
Vitamin D level (D 2 +D 3 ) f	10-19		
ionized or corrected calcium level	low		
dietary calcium intake	normal or low		
PTH*	>65	
 
• 4000 IU/day of vitamin D supplementation x 8 weeks
 
• Vitamin D (D2+D3) level should be checked in 8 weeks
 
• continue Vitamin D supplementation if still low
 
• Once normalized the participant would receive 600 IU/day of Vitamin D
 
	
 
• calcium supplementation at a dose of 50 mg/kg divided 3x/day (max daily calcium dose of 2.000 mg/day) for 4 weeks
 
• Check ionized or corrected calcium level every week and increase supplementation as needed to normalize ionized or corrected calcium
 
• Once ionized or corrected calcium is normalized, if dietary calcium is low, the participant will receive calcium 1,000 mg/day
 

**\* When PTH is <65 and Vitamin D level (D2+D3) is 10-19 with low ionized or corrected calcium and normal or low dietary calcium intake, follow the same supplementation guidelines.**

Age	$\geq 9$	Vitamin D	Calcium (elemental)
Vitamin D level ( $D_2+D_3$ ) T	10-19	
 
• 50000 IU (single dose) every week x 8 total doses
 
• Vitamin D (<math>D_2+D_3</math>) level should be checked in 8 weeks
 
• Continue Vitamin D supplementation if still low
 
• Once normalized the participant would receive 600 IU/day of Vitamin D
 
	
 
• calcium supplementation at a dose of 50 mg/kg divided 3x/day (max daily calcium dose of 2.000 mg/day) for 4 weeks
 
• Check ionized or corrected calcium level every week and increase supplementation as needed to normalize ionized or corrected calcium
 
• Once ionized or corrected calcium is normalized, if dietary calcium is low, the participant will receive calcium 1,200 mg/day
 

ionized or corrected calcium level	low		
dietary calcium intake	normal or low		
PTH*	$>65$		

***\*When PTH is  $<65$  and Vitamin D level ( $D_2+D_3$ ) is 10-19 with low ionized or corrected calcium and normal or low dietary calcium intake, follow the same supplementation guidelines.***

Age	<9	Vitamin D	Calcium (elemental)
Vitamin D level (D 2 +D 3 ) T	10-19	
 
50000 IU (single dose) of vitamin D every other week x 4 total doses.
 
Check Vitamin D (D2+D3) levels in 8 weeks
 
Continue vitamin D supplementation until Vitamin D levels normalize. Once normalized vitamin D would be given as part of multivitamin supplementation.
 
	
 
calcium supplementation a dose of 50 mg/kg/day (max daily calcium dose of 2.000 mg/day) or the maximum allowed per TPN
 
Check ionized or corrected calcium level every week
 

ionized or corrected calcium levels	normal or low		
PTH*	>65		
Oral intake	No		
Patient on TPN	Yes		

**\*When PTH is <65 and Vitamin D level (D2+D3) is 10-19 with normal ionized or corrected calcium, calcium supplementation at a dose of 50mg/kg/day 3 times daily is not needed, otherwise follow the same supplementation guidelines.**

Age	$\geq 9$	Vitamin D	Calcium (elemental)
Vitamin D level (D 2 +D 3 ) T	10-19	
 
50000 IU (single dose) every week x 8 total doses
 
Check Vitamin D (D2+D3) levels in 8 weeks
 
Continue vitamin D supplementation until Vitamin D levels normalize. Once normalized vitamin D would be given as part of multivitamin supplementation.
 
	
 
calcium supplementation a dose of 50 mg/kg/day (max daily calcium dose of 2.000 mg/day) or the maximum allowed per TPN
 
Check ionized or corrected calcium level every week
 

ionized or corrected calcium levels	normal or low		
PTH*	>65		
Oral intake	No		
Patient on TPN	Yes		

**\*When PTH is <65 and Vitamin D level (D2+D3) is 10-19 with normal ionized or corrected calcium, calcium supplementation at a dose of 50mg/kg/day 3 times daily is not needed, otherwise follow the same supplementation guidelines.**

